5.1.2 Secondary endpoints

The change value of FBG, PPG 2h and HOMA-IR from baseline to 24 Weeks or before antidiabetic therapy initiation within 24 weeks.

The percentage change of LDL-C levels from baseline to 24 Weeks or before antidiabetic therapy initiation within 24 weeks.

The percentage change of non HDL-C levels from baseline to 24 Weeks or before antidiabetic therapy initiation within 24 weeks.

The change value of HbA1c levels from baseline to 12 Weeks or before antidiabetic therapy initiation within 12 weeks.

The change value of FBG, PPG 2h and HOMA-IR from baseline to 12 Weeks or before antidiabetic therapy initiation within 12 weeks.

The percentage change of LDL-C levels from baseline to 12 weeks or before antidiabetic therapy initiation within 12 weeks.

The percentage change of non HDL-C levels from baseline to 24 Weeks or before antidiabetic therapy initiation within 12 weeks.

5.2 Safety Assessments

5.2.1 Clinical Assessment

Baseline clinical and demographic characteristics will be measured at study enrollment. Variables of interest will include gender, age, weight, height, waistline, medical history, family history, smoking status, alcohol intake.

Physical examination:

Blood pressure, heart rate and ECG are measures of various physiological statistics, in order to assess the most basic body functions. Vital signs are also an essential part of a case when the subjects appear SAEs. The act of taking vital signs normally entails recording pulse rate (or heart rate) and blood pressure , but may also include other measurements.

New onset medical conditions:

ASCVD, hypertension, cancer, etc.

5.2.2 Laboratory assessments:

Blood samples for determination of clinical chemistry and urinalysis will be taken at the times indicated in the Study Plan and Time Schedule (see table 1).

The following laboratory efficacy variables will be measured:

Serum lipids (TG/non HDL-C/TC/LDL-C), HbA1c (%), Plasma Glucose (PG), insulin, C-peptide levels at fasting and 2 h after drinking glucose solution(75g glucose)

The following laboratory safety variables will be measured:

Hepatic function (Bilirubin, albumin, liver enzymes), Creatine kinase (CK), Renal function (Serum creatinine, BUN ,eGFR), Routine blood test, Pregnancy test (HCG test for women of childbearing potential only)

Notes: Male eGFR= $170 \times (\text{Scr})^{-1.234} \times (\text{Age})^{-0.179}$

Female eGFR= $170 \times (\text{Scr})^{-1.234} \times (\text{Age})^{-0.179} \times 0.79$

6 SAFETY

6.1 Definition of adverse events and adverse drug reaction

Adverse Events (AE), Adverse drug reaction (ADR), and unexpected adverse drug reaction (UADR) events are all considered as AEs.

6.1.1 Adverse Events

An adverse event is defined as any untoward medical occurrence in a clinical trial subject. The event does not necessarily have a causal relationship with study treatment. The investigator is responsible for ensuring that any adverse events observed by the investigator or reported by the subject are recorded in the subject' s medical record.

The definition of adverse events includes worsening of a pre-existing medical condition. Worsening indicates the pre-existing medical condition has increased in severity, frequency, and/or duration, and/or has an association with a significantly worse outcome. A pre-existing condition that has not worsened during the study, and involves an intervention such as elective cosmetic surgery or a medical procedure while on study is not considered an adverse event.

Overdose should also be considered as an AE.

6.1.2 Adverse Drug Reaction

An ADR is a response to a drug which is noxious and unintended and which occurs at doses normally used for the diagnosis, therapy or treatment of disease or for modification of physiological function. As opposed to an adverse event, is characterized by the fact that a causal relationship between the product and the occurrence is suspected.

An unexpected adverse drug reaction (UADR) is an ADR, the nature or severity of which is not consistent with the applicable product information

6.2 Serious adverse event

An AE is considered a serious AE (SAE) if it fulfills one or more of the following criteria:

- Results in death
- Is life-threatening
- Requires or prolongs hospitalization
- Is a congenital anomaly or birth defect
- Is a persistent or significant disability/incapacity
- Is another important medical event in the opinion of the investigator

The requirement or extension of hospitalization is not considered a SAE if it fulfills one or more of the criteria(see Appendix 2):

SAEs or non-serious AEs that are not study outcomes and are not expected as part of normal treatment and progression of the disease or expected with the treatment with Xuezhikang and atorvastatin, must be reported. All SAEs, all non-serious AEs leading to permanent discontinuation of study-drug treatment and non-serious AEs which the investigator considers of particular concern will be recorded on the Adverse Event Report form.

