6.9 Adverse events based on examinations and tests

Deterioration as compared to baseline in protocol-mandated including laboratory values, vital signs should therefore only be reported as AEs if they fulfil any of the SAE criteria or are the reason for discontinuation of treatment with the investigational product.

If deterioration in a laboratory value/vital sign is associated with clinical signs and symptoms, the sign or symptom will be reported as an AE and the associated laboratory result/vital sign will be considered as additional information. Wherever possible the reporting Investigator uses the clinical, rather than the laboratory term (e.g., anaemia versus low haemoglobin value). In the absence of clinical signs or symptoms, clinically relevant deteriorations in non-mandated parameters should be reported as AE(s). Deterioration of a laboratory value, which is unequivocally due to disease progression, should not be reported as an AE/SAE. Any new or aggravated clinically relevant abnormal medical finding at a physical examination as compared with the baseline assessment will be reported as an AE.

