8.4.3 Safety Endpoints Analyses

Adverse events are coded by using standard terminology. Subject incidences of treatment-emergent adverse events, serious adverse events, treatment-related adverse events and adverse events leading to discontinuation will be tabulated by system organ class and preferred term for each treatment group.

Subgroup analysis of AE tables by the stratification factor, gender, and age will be performed.

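### The protocol gives conflicting rules on which adverse events are recorded, so what feeds the treatment-emergent AE tables in 8.4.3 is not fixed

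*Protocol*

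**What the plan says.** **Narrow rules.** Section 6.2 of the protocol lists what goes on the Adverse Event Report form. Two classes are unconditional: "All SAEs, all non-serious AEs leading to permanent discontinuation of study-drug treatment". The third depends on judgement: "non-serious AEs which the investigator considers of particular concern will be recorded on the Adverse Event Report form". The sentence before sets a reporting duty for "SAEs or non-serious AEs that are not study outcomes and are not expected as part of normal treatment and progression of the disease". That sentence closes with a further exclusion for drug effects already foreseen: "or expected with the treatment with Xuezhikang and atorvastatin, must be reported". Expected events therefore fall outside that duty. Section 6.9 says that deterioration in protocol-mandated laboratory values and vital signs "should therefore only be reported as AEs if they fulfil any of the SAE criteria" or cause study drug to be stopped.

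**Wider rules.** Section 6.1.1 makes the investigator responsible for ensuring that "any adverse events observed by the investigator or reported by the subject are recorded in the subject' s medical record"; it does not mention the CRF. Section 4.2.2 asks for AE information at Visits 2, 3 and 4 with no limit on seriousness. Section 6.4.1 runs AE assessment from consent through the whole study. Section 6.4.3 requires every non-serious ADR to be reported, within 7 calendar days to the company named there. Section 6.5 implies that AEs are entered in the CRF, and 10.5 puts all participant data on it.

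**Analysis.** Section 8.4.3 plans the following: "Subject incidences of treatment-emergent adverse events, serious adverse events, treatment-related adverse events and adverse events leading to discontinuation will be tabulated". The layout of those tables is "by system organ class and preferred term for each treatment group".

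**The concern.** A table of treatment-emergent AEs is only as complete as the record behind it. Section 8.4.3 lists that category alongside SAEs, treatment-related AEs and AEs leading to discontinuation, so it must be meant to hold ordinary non-serious events as well. Those are the events that the 6.2 form rule leaves to discretion.

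The trial is open-label. The safeguards in 1.4.3 and 3.3.3 are blinded outcome adjudication and blinded laboratory work. Neither covers the investigator's decision on whether a symptom is worrying enough for the form, expected, or caused by the drug.

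At stake are the completeness of the tolerability summary and the fairness of its two columns. With about 20 sites, some could follow 6.2 and others 4.2.2 or 10.5. An SAP cannot repair this later, because it cannot recover events that were never entered.

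**Working it through.** The protocol gives no AE rate, so there is no figure to reproduce. The check sets the provisions side by side.

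| Section | Which events | Where they go |
|---|---|---|
| 6.1.1 | Any AE observed or reported | Medical record |
| 4.2.2, Visits 2–4 | AE information, unrestricted | Not stated |
| 6.2, reporting sentence | Events that are neither outcomes nor expected | Must be reported; destination not stated |
| 6.2, form sentence | SAEs; AEs ending drug permanently; non-serious AEs the investigator singles out | Adverse Event Report form |
| 6.4.3 | Every non-serious ADR | The company named there |
| 6.9 | Mandated laboratory or vital-sign worsening, only if serious or stopping drug | Reported as AE |
| 6.5 | Unresolved AEs, no further CRF recording | Implies earlier CRF entry |
| 10.5 | All participant data | CRF |
| 8.4.3 | Treatment-emergent AEs by arm | Source not stated |

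Three conflicts follow.

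1. *Within 6.2.* An unexpected non-serious AE must be reported under one sentence. Under the next it reaches the form only if it ends treatment or the investigator singles it out. In the other direction, an expected SAE is outside the first sentence but inside the second.
2. *6.2 against 6.4.3.* Section 6.2 exempts events expected with the drugs. Section 6.4.3 requires every non-serious ADR, with no such exemption.
3. *6.2 and 6.9 against 8.4.3.* The form rule cannot by itself supply a complete treatment-emergent category, and no section says whether the form is the CRF AE page or a separate safety report.

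The exemption for expected events could also act unequally without any bias on the investigator's part. Section 1.3 gives gastrointestinal effects for Xuezhikang, and gastrointestinal effects, headache and mild muscle pain for atorvastatin. If expectedness is judged drug by drug, a headache could be exempt in one arm and reportable in the other.

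**Illustration, with assumed rates only.** Recorded incidence = true incidence × share of affected subjects recorded. Take a true incidence of 30% in both arms.

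| Share recorded, arm A / arm B | Recorded incidence | Ratio |
|---|---|---|
| 30% / 30% | 0.30×0.30 = 9% / 9% | 1.0 |
| 40% / 50% | 0.30×0.40 = 12% / 0.30×0.50 = 15% | 0.8 |
| 30% / 50% | 9% / 15% | 0.6 |
| 70% / 80% | 0.30×0.70 = 21% / 0.30×0.80 = 24% | 0.875 |
| 60% / 80% | 18% / 24% | 0.75 |
| 50% / 80% | 15% / 24% | 0.625 |

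The ratio equals the ratio of the two recording shares whatever the true common incidence. Equal under-recording leaves the ratio at 1 but understates both arms. The arm labels are arbitrary, because nothing in the protocol says which arm would be recorded less fully.

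**The case against.** The strongest reply is that 6.2 describes a safety-reporting form and does not define the analysis data. The form is named once, under a heading about serious events, and apart from the CRF. Sections 4.2.2, 6.4.1, 6.5 and 10.5 together suggest that all AEs are asked about and entered in the CRF. Section 6.8 covers the recording of AEs in general without a seriousness limit. Section 6.4.3 would catch suspected gastrointestinal or muscle symptoms however expected they are. Section 6.9 restricts only mandated tests: accompanying symptoms, clinically relevant changes in non-mandated parameters and new physical findings are still reported as AEs, and the scheduled laboratory values are collected anyway. Section 8.4.3 states no between-arm test.

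Most of this stands. A reader might infer from 6.2 that ordinary non-serious AEs go uncollected, or that the expected effects of both drugs are removed from the tables. The documents do not support either inference, because 4.2.2, 6.4.3 and 10.5 point the other way and the form is never named as the source for 8.4.3.

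The wider provisions still do not settle the matter. Visit collection does not say what is entered. Section 6.4.3 covers only events suspected to be causal and sends them to a company, and its closing line summarises only what was collected. Section 6.5 shows that some AEs are in the CRF, not which. Section 10.5 is a general statement, while 6.2 is the specific AE rule that a site would look up.

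**Conclusion.** The protocol contradicts itself on which AEs reach the safety tables. This is more than detail left to an SAP, because what sites enter is fixed by the protocol.

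The consequence is conditional. If sites follow 6.2 and 6.9, treatment-emergent AE incidence is understated and open to different recording by arm under open-label judgement. If they follow 4.2.2 and 10.5, it may be complete. Size and direction are unknown. The figures above rest on an assumed 30% incidence and assumed recording shares, and show only how recording alone would move the table.

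A reader might go further and infer a spurious tolerability advantage for Xuezhikang, or a falsely significant difference. Neither follows: no direction can be derived, and the protocol plans a tabulation by arm, not a test.

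**What to change.** Reconcile 6.1.1, 6.2, 6.4.3, 6.9 and 8.4.3:

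- State in 6.1.1 and 6.2 that every AE in the 6.4.1 collection period is entered on the CRF, regardless of seriousness, expectedness or investigator concern.
- Keep the lists in 6.2 only as rules for reporting to the sponsor. Say how the Adverse Event Report form relates to the CRF AE record, and bring the exemption for expected events into line with 6.4.3.
- Word 6.9 so that its limit governs reporting to the sponsor and not CRF entry.
- Name the CRF AE record in 8.4.3 as the source of all the AE tables.

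The cost is protocol wording and modest extra CRF entry. AEs are already scheduled in the Table 1 study plan from Visit 1 to Visit 4, so no visit or procedure is added.

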6.3 Adverse events requiring additional data collection

Adverse events requiring additional data collection are events which, in the evaluation of safety, have a special focus (e.g. required by the health authorities). The AEs requiring additional data collection are:

- Drug-Induced Liver Injury:

ALT or AST >8 ULN

ALT or AST >5 ULN for more than 2 weeks

ALT or AST >3 ULN and (TBL >2 ULN or INR >1.5)

ALT or AST >3 ULN with the appearance of fatigue, nausea, vomiting, right upper quadrant pain or tenderness, fever, rash, and/or eosinophilia (>5%)

- Rhabdomyolysis
- ASCVD
- Cerebrovascular event (stroke or TIA)
- Heart failure requiring hospitalization
- Pancreatitis
- Renal event
- Hypersensitivity reactions
- Acute gallstone disease
- Medication error (concerning trial products):
 - Administration of wrong drug.
 - Note: Use of wrong DUN is not considered a medication error.
- Wrong route of administration.
 - Administration of an overdose with the intention to cause harm (e.g. suicide attempt).

- Accidental administration of a higher dose than intended. A higher dose is a dose of at least one tablet/capsule more than the intended dose; however the administered dose must deviate from the intended dose to an extent where clinical consequences for the trial subject were likely to happen as judged by the investigator, although they did not necessarily occur.

6.4 Collecting and Reporting Serious Adverse Events

6.4.1 Collection period

AE assessment will be conducted from the informed consent signed to the entire study.

6.4.2 Reporting Serious Adverse Events

SAEs should be reported to sponsor within 24h of learning of their occurrence.

The investigator is responsible for continuing to follow all SAE reports (whether related to study drug) until resolution or until the event is considered chronic and/or stable by the investigator and/or other physician who has the responsibility for the patient's medical care. Follow-up SAE reports will be reported according to the same timelines as initial reports, as soon as new significant information becomes available.

If any SAE occurs in patients who took Xuezhikang, investigators or other site personnel should also inform the Sponsor, whether considered causally related to the Xuezhikang.

For fatal or life-threatening adverse events where important or relevant information is missing, active follow-up is undertaken immediately.

In keeping with regulatory guidance, outcome events and expected SAEs are not subject to expedited regulatory reporting will be reported in aggregate. Suspected Unexpected Serious Adverse Reactions [SUSARs] will undergo expedited reporting to relevant regulatory authorities (e.g., research ethics committees, National Medical Products Administration, and National Health Commission of the People's Republic of China). Investigators must report all SUSARs to sponsor as soon as possible and 24h of learning of the event. These SUSARs will be centrally reviewed and reported by the sponsor as soon as possible:

- For fatal or life-threatening SUSARs, sponsor must report as soon as possible and within 7 days of learning of the events. Active follow-up must be completed within the following 8 days (The first day of learning of the event is considered 0 day).

- For fatal or life-threatening SUSARs, sponsor must report as soon as possible and within 15 days of learning of the events.

Send SAE reports to Luye Pharma Group Co., Ltd , via Email: [contact] ;

6.4.3 Reporting of non-serious ADR

Any non-serious ADR occurs in the course of the study must be reported per the China regulation.

If any non-serious ADR occurs in the course of the study, then investigators or other site personnel should inform Luye **within 7 calendar days** when he or she becomes aware of it.

All collected adverse events will be summarised in the final study report.

Send ADR reports to Luye Pharma Group Co., Ltd , via Email: [contact] ;

6.5 Follow-up of unresolved adverse events

Any AEs that are unresolved at the subject's last AE assessment or other assessment/visit as appropriate in the study are followed up by the Investigator for as long as medically indicated, but without further recording in the CRF.

6.6 Overdose

There are no specific antidotes to xuezhikang and atorvastatin; Current experience with drug overuse is limited; a few cases of simvastatin overdose have been reported. In all conditions, there are no sequelae. Monitoring of CK and liver enzymes (ALT, AST) is recommended. Appropriate clinical testing and general supportive treatment should be given.

6.7 Pregnancy

All pregnancies and outcomes of pregnancy should be reported to Luye Pharma Group Co., Ltd , via Email: [contact] .

6.7.1 Maternal exposure

If a subject becomes pregnant during the study, the investigational product should be discontinued immediately.

6.7.2 Paternal exposure

Male subjects should refrain from fathering a child or donating sperm during the study and 4 weeks following the last dose of the investigational drug.

6.8 Adverse events based on signs and symptoms

When collecting AEs, the recording of diagnoses is preferred (when possible) to recording a list of signs and symptoms. However, if a diagnosis is known and there are other signs or symptoms that are not generally part of the diagnosis, the diagnosis and each sign or symptom will be recorded separately.

6.9 Adverse events based on examinations and tests

Deterioration as compared to baseline in protocol-mandated including laboratory values, vital signs should therefore only be reported as AEs if they fulfil any of the SAE criteria or are the reason for discontinuation of treatment with the investigational product.

If deterioration in a laboratory value/vital sign is associated with clinical signs and symptoms, the sign or symptom will be reported as an AE and the associated laboratory result/vital sign will be considered as additional information. Wherever possible the reporting Investigator uses the clinical, rather than the laboratory term (e.g., anaemia versus low haemoglobin value). In the absence of clinical signs or symptoms, clinically relevant deteriorations in non-mandated parameters should be reported as AE(s). Deterioration of a laboratory value, which is unequivocally due to disease progression, should not be reported as an AE/SAE. Any new or aggravated clinically relevant abnormal medical finding at a physical examination as compared with the baseline assessment will be reported as an AE.

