2.3 Safety

According to the routine procedure, adverse events, abnormal physical examination and abnormal laboratory data (ALT, CK, etc.) will be observed after randomization

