4.2.2 Randomization and treatment period (Visit1-Visit4)

Subjects won't be able to eat or drink anything for eight hours before visit 1, visit 2, visit 3 and visit 4.

Visit 1 (Randomization)

1. Before randomization, the investigator should complete the following actions and collect the relevant data:

- Collect general information:

Demographics data: gender, date of birth, education, insurance
- Retrieving and reviewing the Patient Diary
- Collect the information of clinical assessment such as Serum lipids (TG/non HDL-C/TC/LDL-C), HbA1c , Plasma Glucose (PG), PPG, insulin and C-peptide at fasting and 2h after glucose solution (75g glucose) . Hepatic function (Bilirubin, albumin, liver enzymes), Creatine kinase (CK), Renal function (Serum creatinine, BUN ,eGFR), Routine blood test, Pregnancy test (HCG test for women of childbearing potential only),and ECG. According to the results of the above tests, screen the patients again.
- Eligibility criteria: To verify the participants satisfy all the inclusion criteria and without any exclusion criteria.

2. Randomization.

3. Medical history: Including previous medical history, treatment before screening and other comorbidities.

4. Physical examination: blood pressure, pulse rate, weight, height.

5. Collect the information of Concomitant medications.

6. Collect the information of history of adverse events with statins.

7. Collect physical activity information: Physical activity level by for Measurement of a Person's Habitual Physical Activity (IPAQ)

8. Patients should be guided for medication.

9. Distribute study drugs by groups, patients should start the treatment after the day of randomization

Visit 2 (4 weeks after treatment phase)

1. Collect the information of Concomitant medications.
2. Collect the information of adverse events. If any AE is reported, relevant laboratory test should be collected.
3. Collect the information of clinical assessment such as Serum lipids (TG/non HDL-C/TC/LDL-C), Plasma Glucose (PG), PPG, insulin and C-peptide at fasting and 2h after drinking glucose solution (75g glucose) . Hepatic function (Bilirubin, albumin, liver enzymes), Creatine kinase (CK), Renal function (Serum creatinine, BUN ,eGFR).
4. Collect physical activity information: Physical activity level by for Measurement of a Person's Habitual Physical Activity (IPAQ)
5. Patients should be guided for medication and lifestyle
6. Review of the patient's diary, compliance to study medication

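### Section 6.9 gives two incompatible adverse-event rules for symptom-free blood-pressure and pulse findings that are not recorded as a diagnosis

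*Protocol*

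**What the plan says.** The opening sentence of Section 6.9 covers "Deterioration as compared to baseline in protocol-mandated including laboratory values, vital signs" and continues that these "vital signs should therefore only be reported as AEs if they fulfil any of the SAE criteria or are the reason for discontinuation" of the investigational product. A noun is missing after *protocol-mandated*, and *including* leaves the list open.

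The middle paragraph deals with two other cases. Where a deterioration comes with symptoms, the symptom is the AE and the measured value is supporting information. Clinically relevant deteriorations in parameters that the protocol does not mandate are AEs even without symptoms.

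The closing sentence reads: "Any new or aggravated clinically relevant abnormal medical finding at a physical examination as compared with the baseline assessment will be reported as an AE".

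Elsewhere the protocol treats the two categories as one:
- Section 4.2.2, Visit 1: "Physical examination: blood pressure, pulse rate, weight, height".
- Section 5.2.1, under its physical-examination subheading: "Blood pressure, heart rate and ECG are measures of various physiological statistics". The same paragraph then describes pulse rate (or heart rate) and blood pressure as the usual vital signs.
- Table 1 in Section 4.1 has a physical-examination row marked at Visits 1 to 4, and no vital-signs row.

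Section 2.3 says that "adverse events, abnormal physical examination and abnormal laboratory data (ALT, CK, etc.) will be observed after randomization". Section 5.2.1 lists among new-onset conditions "ASCVD, hypertension, cancer, etc", without saying whether these are recorded as AEs.

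**The concern.** Many protocols can carry both sentences of Section 6.9 safely, because vital signs and the physical examination are separate procedures there. Here they are the same measurements, so an investigator who sees a clinically relevant but symptom-free rise in blood pressure at a treatment visit can cite the section for either decision.

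The decision feeds the safety comparison. Section 8.4.3 describes that comparison through AE incidence by treatment group. Treatment is open-label (Section 1.4.3), the investigator is told the allocation (Section 3.3.3), and blinding is stated only for outcome adjudication and laboratory work. AE recording is therefore done by people who know the arm, at about 20 sites. If sites settle the ambiguity differently, the affected rows of the AE tables partly reflect the rule applied. An event never entered as an AE cannot be restored to those tables at the analysis stage.

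**Working it through.** The protocol has no figure of its own on this point, so the check compares the texts.

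**Step 1: do the two sentences cover the same measurements?** Blood pressure and pulse rate are expressly physical examination (Sections 4.2.2 and 5.2.1) and expressly vital signs (Section 5.2.1). They are protocol-mandated through Table 1. Both sentences therefore apply to them. Weight is named only as physical examination. It could reach the opening sentence only through the ungrammatical, open-ended scope wording or the remark in 5.2.1 that vital signs may extend to other measurements, so its natural place is the closing sentence. ECG sits under the physical-examination subheading in 5.2.1 but has its own row in Table 1; its position is also less certain.

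**Step 2: for which findings do the rules disagree?**

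| Blood-pressure or pulse finding | Opening sentence | Closing sentence | Conflict |
|---|---|---|---|
| Serious | AE | AE | No |
| Reason for stopping study drug | AE | AE if clinically relevant | No practical conflict |
| With symptoms | Settled by the middle paragraph: the symptom is the AE | Same | No |
| Not clinically relevant, not serious, drug continued | Not an AE | Not required | No |
| Clinically relevant, symptom-free, non-serious, drug continued | Not an AE | AE | **Yes** |

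**Step 3: does any other text settle the last row?** The middle paragraph covers symptomatic cases and non-mandated parameters only. Section 6.1.1 gives a broad AE definition and Section 6.8 prefers diagnoses to lists of signs. Together they let a formally diagnosed hypertension be recorded as an AE whichever sentence of 6.9 is followed. They do not decide what happens to a reading that nobody has turned into a diagnosis. No text gives either sentence precedence.

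**Step 4: is recording consistent downstream?** Section 6.2 says that the Adverse Event Report form takes all SAEs, non-serious AEs that lead to permanent discontinuation, and non-serious AEs that the investigator singles out as a concern. A finding that is an AE under the closing sentence of 6.9 may thus still not reach that form.

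**Step 5: how large could the effect be?** Let p be the proportion of subjects with a finding of the kind in the last row, equal in both arms, and let a and b be the fractions of such findings reported as AEs in the two arms. The difference produced by reporting alone is p × (a − b). It is zero if a = b and at most p in absolute size. The protocol gives none of p, a or b. It gives only the number of planned occasions: Table 1 has 3 on-treatment examinations per subject, so 392 × 3 = 1,176. That is an upper count, because it ignores the 10% dropout assumed in Section 8.1 and relies on Table 1 alone (the Visit 2 to 4 lists in 4.2.2 do not repeat the examination). It counts opportunities and says nothing about bias.

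**The case against.** The strongest reply is that little depends on this. No primary or secondary endpoint is affected. Hypertension is not among the events needing additional data collection in Section 6.3, and Section 2.3 gives ALT and CK as its laboratory examples. Blood pressure is scheduled at every treatment visit in Table 1, so the arms can be compared on measured values whatever is coded as an AE, and an analysis plan not shown here may do so. This stands, and it limits the importance of the point. It does not reconcile the two sentences or make the AE tables uniform.

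A reader might go further and infer that the opening sentence keeps all new-onset hypertension out of the AE data. The documents do not support that: the sentence restricts deteriorations in measured values, and Sections 6.1.1 and 6.8 leave a route for the diagnosis. A reader might also extend the conflict to weight, which is named only as physical examination. Finally, a reader might put a number on a spurious difference between arms. That needs an incidence and an arm-specific reporting rate, and the protocol contains neither. It also gives no evidence that sites would in fact choose differently by arm; open-label treatment only makes that possible.

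Deleting *vital signs* from the opening sentence would not be enough. Blood pressure would remain protocol-mandated and could still be caught by *including*; the rule for symptomatic cases has to be preserved; and Section 6.2 would still govern which AEs reach the form.

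**Conclusion.** The concern holds in a limited form. Section 6.9 gives incompatible AE rules for blood-pressure and pulse findings that are clinically relevant, symptom-free, non-serious, do not stop study drug, and are not recorded as a diagnosis. The conflict is in the current text and follows from the protocol's own definitions, with no outside assumption.

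The consequence is that AE ascertainment for these findings can vary by site or, because treatment is open-label, by arm. The size and direction of any effect on the tables in Section 8.4.3 cannot be computed from the protocol. The HbA1c analysis and the sample size are not involved. The passages should be reconciled because this is cheap and an unreported event cannot later be recovered as an AE; the point does not threaten the trial's main conclusion.

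**What to change.** Reconcile the sentences so that one rule applies in both arms. One workable form:

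1. Limit the opening sentence of Section 6.9 explicitly to protocol-mandated laboratory values, removing both the mention of vital signs and the open-ended *including*.
2. Let the closing sentence govern symptom-free, clinically relevant blood-pressure and pulse findings.
3. Keep the existing rule that in symptomatic cases the symptom is the AE and the measurement is supporting information.
4. State that new-onset hypertension, listed in Section 5.2.1, is recorded as an AE.
5. Align Section 6.2 with this, so that it is clear which non-serious AEs are entered on the Adverse Event Report form.

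The cost is a short protocol amendment, a somewhat higher AE count in both arms, and slightly more data entry. No new measurement or visit is needed.
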